Attachment C-R: Milestone Schedule

	Milestone Name	Description	Projected Completion Date
A	Project Start Date	-	3/13/2017
B1	Stakeholder engagement meeting	Stakeholder engagement kick-off meeting	3/30/2017
B2	Patient eligibility data pulls	EIS Data Analyst to create a list of eligible patient population	4/30/2017
B3	Study protocol completed	Final trial protocol completed - submit a copy to PCORI	5/30/2017
B4	Patient eligibility data pulls	EIS Data Analyst to finalize list of eligible patient population and other data pulls	5/30/2017
B5	IRB Approval Obtained	Obtain IRB approval for study and submit approval letters to PCORI	7/30/2017
B6	DSMB Meeting 1	Set safety protocols and standards for data safety monitoring	7/30/2017
B7	Integration of questionnaires into patient portal	EIS Data Analyst to integrate questionnaires into MyCSLink	7/30/2017
B8	Select and register project at appropriate site for the study design (Clinicaltrials.gov, RoPR, or other as approved by PCORI before study start date)	Study Identification Number and the Primary Research Completion Date must be sent to PCORI.	7/30/2017
B9	Randomization of clinic sites	Randomization of Cedars-Sinai network offices completed; 50% to CDS arm and 50% to PEAT arm of trial	7/30/2017
B10	Passive patient recruitment begins	Passive data enrollment begins for study participants (N=960) / Study begins	8/1/2017
B11	Pharmacy data collection begins	EIS Data Analyst to begin pull data for passively enrolled patients on pharmacy data for data monitoring purposes	8/1/2017
B12	Patient baseline questionnaires	Enrolled patients begin filling out PROMIS patient reported outcome questionnaires	8/1/2017
B13	Stakeholder engagement meeting	Stakeholder engagement meeting to update on IRB submission and patient eligibility protocols and baseline data collection	8/31/2017
B14	Engagement Update	For the 6-month time intervals (i.e., 6 months, 18 months, 30 months, etc. but not at 12 months or 24 months), provide specific examples of the impact of engagement on project activities during the reporting period. Report this in the Engagement Report section of the PCORI interim progress report.	9/13/2017
B	Report Submission	Submit 6-month Interim Progress Report, Using PCORI Interim Progress Report Template	9/13/2017
C1	Study intervention begins	Study intervention begins	1/1/2018
C2	Stakeholder engagement meeting	Updates on study implementation	2/28/2018
C3	DSMB Meeting 2	Review safety monitoring standards and plan interim data analysis	3/1/2018
C4	Engagement Report	For each annual report (i.e., at year 1, year 2, etc. but not at 6 months or 18 months), additional descriptive information on engagement of patients and/or other stakeholders should be reported at https://live.datstathost.com/PCORI-Collector/Survey.ashx?Name=Engagement_Report_Login . Confirmation code should be reported in the Engagement Report section of the PCORI interim progress report.	3/13/2018
C	Report Submission	Submit 12-month Interim Progress Report, Using PCORI Interim Progress Report Template	3/13/2018
D1	25% enrollment	Completion of 25% of study enrollment/recruitment (240/960)	6/15/2018

D2	50% enrollment	Completion of 50% of study enrollment/recruitment (480/960)	8/15/2018
D3	Pharmacy data collection continues	EIS Data Analyst to pull monthly for enrolled patients on pharmacy data for data monitoring purposes.	9/13/2018
D4	Engagement Update	For the 6-month time intervals (i.e., 6 months, 18 months, 30 months, etc. but not at 12 months or 24 months), provide specific examples of the impact of engagement on project activities during the reporting period. Report this in the Engagement Report section of the PCORI interim progress report.	9/13/2018
D	Report Submission	Submit 18-month Progress Report, Using PCORI Interim Progress Report Template	9/13/2018
E1	75% enrollment	Completion of 75% of study enrollment/recruitment (720/960)	10/15/2018
E2	100% enrollment	Completion of 100% of study enrollment/recruitment (960/960)	12/31/2018
E3	Interim analysis	Data cleaning, linking, merging, specification of statistical models, data dictionary and codebook development	1/31/2019
E4	Stakeholder engagement meeting	Review of interim data analysis, study implementation, missing data issues, potential safety issues	1/31/2019
E5	DSMB Meeting 3	Board reviews interim data analysis to examine potential safety issues	1/31/2019
E6	50% follow-up data collection	Completion of 50% of follow-up data collection	2/1/2019
E7	Pharmacy data collection continues	EIS Data Analyst to pull monthly for enrolled patients on pharmacy data for data monitoring purposes	3/13/2019
E8	Engagement Report	For each annual report (i.e., at year 1, year 2, etc. but not at 6 months or 18 months), additional descriptive information on engagement of patients and/or other stakeholders should be reported at https://live.datastathost.com/PCORI-Collector/Survey.ashx?Name=Engagement_Report_Login . Confirmation code should be reported in the Engagement Report section of the PCORI interim progress report.	3/13/2019
E	Report Submission	Submit 24-month Interim Progress Report, Using PCORI Interim Progress Report Template	3/13/2019
F1	75% follow-up data collection	Completion of 75% of follow-up data collection	6/15/2019
F2	DSMB Meeting 4	Board reviews data collection	7/30/2019
F3	Stakeholder engagement meeting	Update on intervention, data collection	7/28/2019
F4	Engagement Update	For the 6-month time intervals (i.e., 6 months, 18 months, 30 months, etc. but not at 12 months or 24 months), provide specific examples of the impact of engagement on project activities during the reporting period. Report this in the Engagement Report section of the PCORI interim progress report.	9/13/2019
F	Report Submission	Submit 30-month Interim Progress Report, Using PCORI Interim Progress Report Template	9/13/2019
G1	Stakeholder engagement meeting	Discussion of preliminary research findings and implementation issues	10/25/2019
G2	Completion of follow-up data collection	Completion of follow-up data collection (100%).	12/15/2019
G3	EHR data pull	Final data pull from EIS Data Analyst with all encounters, covariates, and pharmacy data	12/15/2019
G4	Statistical analysis	Data cleaning, linking, merging, specification of statistical models, data dictionary and codebook development	1/30/2020
G5	Primary completion date	A Primary Research Completion Date must be provided when registering the study in Clinicaltrials.gov. For studies that are not clinical trials or observational studies registered on ClinicalTrials.gov, the Awardee and PCORI shall agree on a primary completion date as a milestone that precedes the agreed-upon date to submit a Draft Final Research Report.	1/30/2020

G6	Stakeholder engagement meeting	Discussion of findings and implications, Creation of detailed dissemination strategy and specific roles of each team member	2/3/2020
G7	Website development	Development of sub-site with study findings and implications	2/30/2020
G8	Engagement Report	For each annual report (i.e., at year 1, year 2, etc. but not at 6 months or 18 months), additional descriptive information on engagement of patients and/or other stakeholders should be reported at https://live.datstatshost.com/PCORI-Collector/Survey.ashx?Name=Engagement_Report_Login . Confirmation code should be reported in the Engagement Report section of the PCORI interim progress report.	3/13/2020
G9	Website launch	Launch of study findings website	3/13/2020
G10	Patient-facing reports development	Development of patient-facing reports by Patient Partners and Investigators	3/13/2020
G11	Manuscript development	Development of primary outcome/specific aim manuscripts	3/13/2020
G12	Press release development	Collaboration with Patient Partners to create press releases for lay media	3/13/2020
G13	Dissemination presentations	Presentations by Investigators and Patient Partners	3/13/2020
G14	De-identified dataset	EIS Data Analyst to create de-identified dataset for data sharing	3/13/2020
G15	Stakeholder engagement meeting	Discussion of next steps and future dissemination activities	3/13/2020
G	Research Project Period End Date		3/13/2020
H	Final Progress Report Submission	Submit Final Progress Report, Using Final Progress Report Template. Submit Expenditure Report (See Contract for Instructions)	3/13/2020
I	Results submitted to ClinicalTrials.gov or appropriate database.	Awardee ensures results are submitted to ClinicalTrials.gov or appropriate database. For ClinicalTrials.gov, the generated tables are a required section in the Draft Final Research Report.	9/1/2020
J	Draft Final Research Report Submission	Submit Draft Final Research Report according to instructions found at http://www.pcori.org/awardee-resources *Draft Final Research Report must be submitted no later than 30 days from when results are posted to clinicaltrials.gov or other applicable website.	10/1/2020
K	Final Research Report	Upon receipt of written summary, and as applicable, PI will make revisions and submit revised Draft Final Research Report for acceptance as directed by PCORI.	See Description
L	Approval / sign off of the Lay Abstract	Sign off must be no later than 90 days beyond the date PCORI accepts the final report	3/31/2021
M	Contract Term End Date		3/31/2021
N	Final Expenditure Report	Submit Final Expenditure Report (See Contract for Instructions) 90 days from Contract Term Date	6/30/2021

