- (1) *Discussion of Risks and Benefits of Opioid Analgesics as Long-Term Therapy for Patients with Chronic Pain and Establishment of a Treatment Goal.* This alert is triggered whenever a refill for a long-acting or extended-release opioid is entered or when any new opioid prescription is ordered.
- (2) *Evaluation of Risk Factors for Opioid-Related Harms.* This alert is triggered whenever there is an existing diagnosis of prior substance abuse disorder, history of overdose, history of sleep apnea, renal or hepatic insufficiency, age over 65 years, or a diagnosis of depression, anxiety disorder, or Post-Traumatic Stress Disorder in the setting of opioid use.
- (3) *High-Risk Opioid Co-Prescribing: Co-Prescribing of Benzodiazepines and Opioids.* This alert is triggered whenever an order for a benzodiazepine is entered in the setting of a preexisting opioid prescription, or vice versa.

Figure 2 presents a schematic demonstrating the process flow for a CDS alert, using the example of the co-prescribing alert. The process begins when a provider places the medication order in the EHR. The Choosing Wisely algorithm, powered by Stanson Health, a CDS developer used by Cedars-Sinai to power its EHR alerts (www.StansonHealth.com), then evaluates over 30 patient-level data elements to determine whether an alert should be triggered. If there is evidence of potentially inappropriate co-prescription, then the EHR displays a “pop-up” reminder with language supported by Choosing Wisely guidelines. The provider may override the alert by selecting one of several pre-populated reasons (e.g. “end-of-life care”) and the system records the rationale. The system also allows the provider to offer open-ended comments explaining the reason for override. Conversely, the provider may choose to cancel the order and back out from initiating a prescription. Through an analytics dashboard supported by Stanson Health and already used by our health system to monitor system performance with Choosing Wisely alerts, we will track: (1) which provider activated the alert, (2) whether the provider overrode the alert or canceled the order, and (3) for which patient

the alerts were triggered. In this manner, the system offers hard metrics that are already embedded and operating within our EHR data analytics system, offering real-time process measures for the CDS arm.

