E5.c. Power Calculations. Guided by previous work in chronic pain interventions,¹⁴⁰ we calculated sample size using an intracluster correlation coefficient of 0.02, an α level of 0.05, 90% power, and detection of a mean (SD) difference of 0.3 standard deviations on the PROMIS Pain Interference scale. We calculated a sample size of 320 patients per study arm, for a total of 640 patients. To compensate for predicted loss to follow-up, multiple variables in the final multi-level models, as well as sub-group analyses, we inflated the sample size by 50% to 960. Since we will be examining the effect of the interventions on a variety of sub-groups within the study sample, such as diagnoses of mental health conditions, race, ethnicity, gender, and chronic pain diagnosis, we will be adequately powered to detect meaningful differences. In our original proposal, we calculated a sample size of 320 patients per study arm for a total of 640 patients. To compensate for predicted loss to follow-up and non-response we had inflated the recruitment target size by 50% to 960. Under the current modification – and given the absence of changes to the assessment schedule, the estimated intracluster correlation coefficient, and the expected mean difference - the sample size required to adequately power the analysis remains unchanged. We believe the recruitment target will also remain consistent, and potentially even fall due to the ability of study staff to call passively enrolled patients and remind them to respond to assessments. We therefore anticipate being adequately powered to detect meaningful differences between the two arms.

E6 Heterogeneity of Treatment Effect (HT-1, HT-3, HT-4)

After reviewing the literature and consulting with our patient partners, we identified specific subgroups we plan to analyze to identify whether there is a heterogeneity of the treatment effects. Below we detail our planned sub-group analyses, our hypotheses, and our plans for statistical analysis for each subgroup. In order to address the problem of multiplicity, a Bonferroni correction will apply to all analyses.

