b. Statistical Methods to Handle Missing Data and Sensitivity Analyses. If the data is not missing at random, we will use multiple imputation techniques to impute missing data for respondents (MD-2). We plan on using the *mi impute mvn* command in Stata and will generate 20 datasets compatible with the regressions planned for the final analyses. To insure that the imputation has proceeded as expected, we will visually inspect parameters from successive iterations of the model to determine if they have reached a stationary distribution. We will conduct sensitivity analyses with the dataset that includes imputed data as well as with a dataset that does not include imputed data to determine the effect of the multiple imputation and plan on reporting both results. These precautions will serve to identify autocorrelation in the imputed data and allow for proper maintenance of uncertainty in imputed values (MD-3).

c. Reporting Reasons for Dropout and Missing Data. We will drop data from patients who do not have any visits with their PCP during the intervention period or are lost to follow-up, but will compare descriptive statistics for these patients to patients with at least one visit to their PCP for sensitivity analysis (MD-4, MD-5).

E9. Project Milestones and Timeline.

During the first 3-6 months of the study project, we will train the project staff, refine the study protocol, develop the data dictionaries, and obtain IRB approval. We will hold monthly meetings with our patient partners to finalize the study design and discuss issues related to IRB approval. In Year 1, Q4, we will passively enroll eligible patients in the two study arms. In the 4 weeks before the intervention period, we will send baseline questionnaires via REDCap. In Year 2, we will begin the intervention. We will conduct weekly reports from our EHR data warehouse to determine enrolled patient visits. Enrolled patients will be sent CG-CAHPS survey one day after each primary care visit. Enrolled patients will also receive the PROMIS questionnaires once a month. We will perform monthly checks to assess the completeness of data to minimize missing data and will complete one set of interim data analyses in Year 2 to assess whether there are any issues with missing data. Full data analysis will

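### The enrolment milestones contradict the pre-intervention baseline in section E9: on that schedule at least 720 of 960 patients enter after the intervention has started

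*Combined protocol and SAP*

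**What the plan says.** Section E9 of the project plan (Attachment A-R1) puts passive enrolment in the last quarter of Year 1 and the intervention in Year 2. On baseline it says: "In the 4 weeks before the intervention period, we will send baseline questionnaires via REDCap". Under that text, enrolment and baseline both precede exposure.

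The milestone schedule (Attachment C-R) reads differently. Its labels overlap with section numbers, so they are called milestones here.

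- Milestone B4: list of eligible patients finalised, 5/30/2017.
- Milestone B9: randomisation, 7/30/2017.
- Milestones B10 and B12: passive enrolment opens and PROMIS questionnaires begin, 8/1/2017.
- Milestone C1: "Study intervention begins", 1/1/2018.
- Milestone D1: "Completion of 25% of study enrollment/recruitment (240/960", 6/15/2018.
- Milestone D2: "Completion of 50% of study enrollment/recruitment (480/960", 8/15/2018.
- Milestone E1: "Completion of 75% of study enrollment/recruitment (720/960", 10/15/2018.
- Milestone E2: "Completion of 100% of study enrollment/recruitment (960/960", 12/31/2018.

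Three other places matter. Section D2 defines eligibility by the duration, number or dose of opioid prescriptions, with no index date for those counts. The first CDS alert fires on refills of certain opioids "or when any new opioid prescription is ordered". Section E5.b lists baseline HRQOL as a potential covariate in Models 1 and 2, and Models 3 to 5 take their covariates from Model 2.

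**The concern.** The two timelines imply different analysis cohorts and different baseline variables for the primary outcome. Nothing says what baseline means for a patient whose first PROMIS score arrives in, say, October 2018, or whether time in the growth model runs from intervention start or from entry. The primary longitudinal model needs both.

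A score taken after the tools are in use may already carry part of their effect. Adjusting for it as a baseline covariate can then remove part of the difference the trial is meant to estimate. Separately, if patients can still become eligible during 2018, entry depends on opioid prescribing, which the CDS alerts are designed to change. The CDS arm could then differ from the PEAT arm in who is in it.

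**Working it through.** **The plan's own figures.** Section E5.c needs 640 patients and says "we inflated the sample size by 50% to 960": 640 × 1.5 = 960. The milestone fractions agree: 240/960 = 25%, 480/960 = 50%, 720/960 = 75%.

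**Dates relative to intervention start (1/1/2018) and randomisation (7/30/2017).**

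| Milestone | Date | Days from start | Days from randomisation | Still to enrol |
|---|---|---|---|---|
| B4 | 5/30/2017 | −216 | −61 | 960 |
| B10/B12 | 8/1/2017 | −153 | 2 | 960 |
| D1 | 6/15/2018 | 165 | 320 | 720 (75%) |
| D2 | 8/15/2018 | 226 | 381 | 480 (50%) |
| E1 | 10/15/2018 | 287 | 442 | 240 (25%) |
| E2 | 12/31/2018 | 364 | 519 | 0 |

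On schedule, 960 − 240 = 720 patients enter after day 165. How many of the first 240 enter before 1/1/2018 is not stated, so the number entering after the start lies between 720 and 960 (75% to 100%). If accrual is assumed linear from 8/1/2017 to 6/15/2018 (318 days, of which 153 precede the start), 240 × 153/318 = 115 enter before it and 960 − 115 = 845 (88%) after it.

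**Staggered entry or a slip in the dates?** Follow-up has its own milestones: 50% on 2/1/2019 (E6), 75% on 6/15/2019 (F1) and 100% on 12/15/2019 (G2). From E2 to G2 is 349 days, about 11.5 months, which fits roughly a year of follow-up after the last entry. Section E4.e also has questionnaires sent to eligible patients with visits once the intervention period is under way. A year misprint does not fit: 6/15/2017 would precede IRB approval (7/30/2017) and the opening of enrolment (8/1/2017).

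**What the milestones may count.** Section E4.d auto-enrols all eligible patients, about 4,000, and expects about 30% to complete every questionnaire: 0.30 × 4,000 = 1,200. A target of 960 is 960/4,000 = 24% of the eligible pool, so it looks like a count of responders. Milestone B10 attaches N=960 to passive enrolment itself, which leaves some doubt.

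- *First responders.* The first PROMIS score of at least 720 patients falls more than five months after the start. Auto-enrolled patients in either arm may have met their tool by then. Response could also differ by arm, because only PEAT patients receive materials through REDCap, the channel that carries the questionnaires.
- *Newly eligible patients.* If the B4 list is not closed, alerts on new opioid orders can alter who meets the undated criteria in section D2. This route is shown for CDS only: PEAT materials go, two days before a visit, to patients already notified of their inclusion.

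**The case against.** The strongest reply is that most of the dated text points to enrolment before exposure. B4 finalises the list before randomisation, B10 and B12 open enrolment and baseline five months before the intervention, E9 puts both before it, and section D2 counts prior visits in the year before study start. On this view the later milestones are badly labelled and only the wording needs correcting.

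Part of this stands. The documents contradict themselves; they do not settle on late entry. Enrolment after randomisation is not harmful in itself if the list was closed first. Patients who already met the criteria cannot be kept out by a later alert, and auto-enrolment from the EHR limits recruiter discretion.

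The labelling defence does not go through. The milestones cannot simply be re-read as follow-up response, because E6, F1 and G2 already count follow-up. Nor does a closed B4 list remove the difficulty: it answers the eligibility route, but not the dating of the first score.

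A reader might infer that either tool can alter eligibility. The documents support that route only for CDS. A reader might also want the harm expressed in standard deviations of pain interference. The plan gives neither the share of qualifying prescriptions an alert would avert nor how those patients' scores differ. A shift in starting scores would in any case not be a bias estimate for a model of change over time.

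**Conclusion.** The contradiction is real and reaches the primary model. On the schedule as written, at least 720 of 960 patients (75%), and possibly all of them, enter after exposure has begun in their physician's practice. This assumes that 25% enrolment is not reached before its projected date and that the contrast between arms begins on 1/1/2018.

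On the likelier reading, the baseline HRQOL covariate, if used, is post-exposure for most patients in Models 1 to 5. On the other reading, entry to the CDS arm is open to influence by the alerts. The size of either bias cannot be derived from the documents.

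It would go too far to say that 75% of patients will enter late, or that the arms will be non-comparable. E9 says otherwise, and whether the B4 list is closed is not stated. The matter should still be settled before analysis, because using post-exposure baselines cannot be fully undone afterwards. The retroactive exclusion of patients with no visit in the study period is a separate post-randomisation criterion, which this point does not cover.

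**What to change.** 1. Reconcile section E9 with milestones B4, B10/B12 and D1 to E2, and state what D1 to E2 count, for example first questionnaire response.
2. Define the primary-analysis cohort, in both arms, as the EHR-eligible list frozen on one stated date before 1/1/2018. Report patients who become eligible later separately.
3. Accept as baseline only PROMIS Pain Interference scores dated before 1/1/2018. Treat later first scores as follow-up outcomes, with time counted from intervention start, and state the 12-month window in section E5.b relative to that origin.
4. Handle missing baselines within the likelihood-based longitudinal model, with baseline as an outcome that has a common mean across arms. Add a sensitivity analysis restricted to patients with a pre-intervention score.

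Routine-care PROMIS data cannot fill the gap. The three scales described as already administered in section E6.d are Physical Function, Depression and Global Health items, not Pain Interference.

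The cost is mainly wording, since an eligible list is already due on 5/30/2017. Patients becoming eligible in 2018 leave the primary analysis, including some new users whom section D2 wants to reach. Some precision is lost where baseline is missing, and patients who first respond late in 2018 contribute few scores to a window of 12 months from the start.

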E4.e. Data Collection (RQ-2). Upon auto-enrollment, we will extract the following variables from the electronic health record: chronic pain condition, length of time with chronic pain diagnosis, race and ethnicity, language, marital status, history of pharmacologic treatment, surgical history related to chronic pain condition, past injuries related to chronic pain condition, and length of time with current primary care provider¹³⁷. When the intervention period is initiated, all eligible patients who have any follow-up visits during this 12-month period in both study arms will be sent the questionnaires. We will also capture depression scores via the Patient Health Questionnaires -PHQ-2 and/or PHQ-9 in the EHR. Furthermore, to determine if conversations about opioid medications took place during the visit that was

informed by either the CDS or the PEATS, we will conduct a structured review of a random sample of charts from both study arms.

E5. Statistical Analysis

E5.a. Descriptive and Exploratory Analyses. We will use frequencies and means for univariate descriptive analyses. We will use chi-square tests and paired t-tests to determine whether there are differences between the two study arms; using these bivariate analyses, we will identify covariates and patient- and physician-level moderators to use in the regression models. We will also consult with our Patient Partner to ensure that all appropriate patient-level covariates are included in the final models.

E5.b. Multi-Variate Regression Models. To evaluate the effectiveness of the comparators on the selected outcomes, we will use hierarchical linear regression models to measure changes in the outcomes over time using growth modeling statistical techniques¹³⁸ and will adjust for clustering at the patient, provider, and provider office level. Growth modeling allows the testing of individual differences in outcomes over time. In this study, we will examine HRQOL and communication scores over 12 months for the two study arms. We will adjust for patient- and provider-level covariates to account for potential confounders and also to identify whether there is heterogeneity of the treatment effect (see below). The proposed models are outlined here. We will test both fixed effects and random effects.¹³⁹ (IR-3):

Primary Outcome: Model 1: Hierarchical Linear Model (Longitudinal Analysis)

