Question: Which communication strategy used during the clinical encounter is more effective in reducing pain interference over time for patients with chronic pain who were taking opioids at baseline?

Dependent variable: Pain interference as measured by PROMIS Pain Interference Score (T-Score, Continuous)

Independent variable: Comparator received, CDS vs. PEAT (Dichotomous)

Potential Covariates: Age, gender, race, ethnicity, mental health comorbidities, chronic pain diagnosis, use of other pain medications (neuropathic pain medications, NSAIDS, antidepressants), benzodiazepine use, number of office visits during intervention period, baseline HRQOL, encounter month, physician years of practice, physician gender, employment, SES.

Moderator Analyses: We will use statistical interactions examining the moderating effects of patient age, race, ethnicity, mental health comorbidities, chronic pain diagnosis, physician years of practice and physician gender on the relationship between comparator and pain interference.

Mediation Analyses: We will test whether confidence in decision and satisfaction with communication as measured by COMRADE Scores mediates the relationship between the comparator used and the pain interference outcomes.

Primary Outcome: Model 2: Hierarchical Linear Model (Longitudinal Analysis)

Question: Which communication strategy used during the clinical encounter is more effective in improving how satisfied patients feel over time after communicating with their physician about chronic pain treatment risks and benefits?

Dependent variable: CG-CAHPS

Independent variable: Comparator received, CDS vs. PEAT (Dichotomous)

Potential Covariates: Age, gender, race, ethnicity, educational level, mental health comorbidities, chronic pain diagnosis, use of other prescribed pain medications (neuropathic pain medications, NSAIDS, antidepressants) benzodiazepine use, number of office visits during intervention period, baseline HRQOL, encounter month, physician years of practice, physician gender, employment, SES.

Subgroup Analyses: We will use statistical interactions examining the moderating effects of patient age, race, ethnicity, education level, mental health comorbidities, chronic pain diagnosis; and physician years of practice and gender on the relationship between comparator and pain interference.

Secondary Outcome: Model 3: Hierarchical Linear Model

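### The schedule places model specification at the interim and again after the final data pull, and Section E5 leaves the primary model open, so it could be chosen after outcome data are seen.

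*Combined protocol and SAP*

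**What the plan says.** **Timing (Attachment C-R, Milestone Schedule).** Milestone E3, the interim analysis, is due 1/31/2019 and is described as "Data cleaning, linking, merging, specification of statistical models, data dictionary and codebook development". Milestone G4, the statistical analysis, is due 1/30/2020 and carries the same description. On the E3 date stakeholders also meet (E4) for "Review of interim data analysis, study implementation, missing data issues, potential safety issues", and the DSMB reviews the interim analysis for safety (E5). Before G4 come a stakeholder meeting on 10/25/2019 (G1), "Discussion of preliminary research findings and implementation issues", and on 12/15/2019 (G3) the "Final data pull from EIS Data Analyst with all encounters, covariates, and pharmacy data".

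**Content (Project Plan, Sections E5.a and E5.b).**
- Effects structure: "We will test both fixed effects and random effects". No rule is given for which is primary.
- Covariates and moderators: after chi-square and t-tests between the arms, "using these bivariate analyses, we will identify covariates and patient- and physician-level moderators to use in the regression models".
- The Model 1 list is provisional: "Potential Covariates: Age, gender, race, ethnicity, mental health comorbidities, chronic pain diagnosis", followed by further items.
- The list stays open to later input: "We will also consult with our Patient Partner to ensure that all appropriate patient-level covariates are included in the final models".

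**What is fixed.** E5.b sets the model family (a hierarchical linear growth model), the Model 1 outcome (PROMIS Pain Interference T-score), the comparison (CDS against PEAT) and adjustment for clustering by patient, provider and office.

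**The concern.** A primary analysis protects the type I error only if it is settled before anyone who can shape it sees outcomes by arm. Here the only scheduled times for specifying the models are at the interim and after the final pull. Several elements are open at both times: fixed or random effects, the covariates, the time function, and whether the primary test is a difference in level or in slope. Each could move the estimate or its standard error.

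Some of those who see the data may also influence the model. The Patient Partner is to be consulted on covariates for the final models. Patient Partners also belong to the stakeholder group, which is to review interim data and discuss preliminary findings. Nothing says that these reviews will be pooled across arms.

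At stake is whether a positive result on pain interference can be read at its nominal level. In addition, one candidate structure, fixed effects for PCPs, would remove one of the possible primary contrasts.

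**Working it through.** **1. Order of events.**

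| Milestone | Date | Days before G4 |
|---|---|---|
| E3 interim, model specification | 1/31/2019 | 364 |
| G1 preliminary findings discussed | 10/25/2019 | 97 |
| G3 final data pull | 12/15/2019 | 46 |
| G4 statistical analysis, model specification | 1/30/2020 | 0 |

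Outcome data exist well before G4. The intervention starts 1/1/2018 (C1), and half of follow-up collection is due 2/1/2019 (E6), one day after E3. The schedule contains no milestone for locking an analysis plan. B3 (5/30/2017) completes the protocol, but the E5 text supplied leaves the choices above open.

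**2. What fixed effects would do to the arm term.** Section E4.d gives 80 PCPs. Suppose each PCP has one arm.
- 80 PCP indicators plus one arm column make 81 columns. The arm column is the sum of the indicators for the PCPs in that arm, so the rank is 80. A time-constant arm effect cannot be estimated.
- 80 PCP indicators plus time and arm-by-time make 82 columns. Arm-by-time varies within a PCP, so the rank is 82. A difference in slope can be estimated.

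The same algebra applies to office indicators only if offices were the unit randomised. Section E4.b first says that randomisation is by provider, then that offices are assigned to arms. Milestone B9 refers to clinic sites and network offices. If PCPs were randomised, arm can vary within an office and office indicators need not absorb it.

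**3. Illustrative cost of choosing between two analyses.** The plan gives no figure to reproduce. Section E5.c states alpha 0.05 without sidedness; two-sided is assumed. If the more favourable of two analyses is reported, and the two null statistics are bivariate normal with correlation r:

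type I error = 1 − P(|Z1| < 1.96 and |Z2| < 1.96)

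| r (assumed) | Type I error |
|---|---|
| 0.80 | 7.8% |
| 0.90 | 7.0% |
| 0.95 | 6.5% |
| 1 (limit) | 5.0% |

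The documents give no value for r. The limit matters. With complete, balanced monthly data and random intercepts only, the arm-by-time estimate comes entirely from within-patient change. Fixed and random PCP intercepts then give the same answer, and choosing between them costs nothing. Choices among covariate sets, or between a level and a slope contrast, need not agree so closely.

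**The case against.** **Specification may mean programming.** The phrase sits beside data cleaning and codebook work, is identical in both rows, and could refer to coding the models already listed in E5.b. Likewise, fixed and random effects may be components of one mixed model. Both readings are plausible. But E5.b does not define a single model, so someone must still choose, and no earlier time for that choice is scheduled. If these readings are intended, stating them would settle the wording, though not the open covariates and effect term.

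**The interim is for other purposes.** Section E9 gives its aim as checking for missing-data problems, and the DSMB's review is for safety. No comparison of the primary outcome by arm is described there, and a shared projected date does not show that specification follows viewing. This stands for E3. It does not cover G4, which follows both the preliminary-findings meeting and the final pull.

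**The identification problem is limited.** Model 1 asks about reducing pain interference over time, so arm-by-time is the natural effect, and PCP fixed effects leave it estimable. This stands. What remains is that the plan never names that term as primary.

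**Bonferroni covers it.** Section E6 applies the correction to all analyses. The sentence appears under heterogeneity of treatment effect and gives no number of tests. It does not address a choice among versions of one primary model.

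**Conclusion.** The point holds as a gap in pre-specification. Followed as written, the plan schedules specification of its models after preliminary findings have been discussed and the final data are in hand. It gives no rule for the effects structure, no final covariate set and no primary effect term. Model family, outcome, comparison and clustering levels are fixed, so the freedom is partial.

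Three stronger readings are tempting and are not supported:
- That the investigators intend to choose on results. The documents permit this but do not say it.
- That fixed effects would make the treatment effect inestimable altogether. That is true only of a time-constant effect with indicators for the randomised unit; for offices it depends on a conflict that the documents leave unresolved.
- That 6.5% to 7.8% is the size of the problem. Those figures rest on assumed correlations of 0.95 to 0.80 and on the better result always being reported. The inflation cannot be derived from the documents and would be close to nil where the two statistics nearly coincide.

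The plan should be changed because the correction is cheap and protects the primary claim, not because a particular error rate has been shown.

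**What to change.** 1. Add a dated SAP lock to the milestone schedule, before any arm-level outcome data are reviewed and so before 1/31/2019. Remove model specification from E3 and G4.
2. In that SAP, replace the plan to try both kinds of effects, and the bivariate covariate selection, with one primary model:
   - arm, time and arm-by-time as fixed effects, with the time function stated and the primary contrast named;
   - random effects for patient, PCP and office, as E5.b already promises, including the unit actually randomised and a random time slope at that level;
   - a fixed covariate list that includes baseline pain interference.
3. Reconcile E4.b with milestone B9 on the unit of randomisation, since the random-effects structure depends on it.
4. Label every other structure or covariate set a sensitivity analysis.
5. Show stakeholders interim and preliminary data pooled across arms.

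The cost is SAP wording and an earlier date for work already planned. The downside is less freedom to adapt the model after seeing the data; any later change would be reported as a deviation or a sensitivity analysis.
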